8. STUDY DESIGN

a. Background or rationale for this study.

Whole blood transfusion was used in World War I, World War II, Korea and Vietnam. By the end of the Vietnam conflict, whole blood had been separated into components for ease of use and more focused transfusion. As a result, transfusion practices did not catch up with the available units. More recent investigations have revealed that patients have fewer deaths from hemorrhage when the ratios of FFP:RBC units and platelet:RBC units approaches 1:1. Furthermore, the success of “walking blood banks” with fresh whole blood transfusion in the 2nd Iraq war and the war in Afghanistan have prompted new interest in the civilian use of whole blood. While civilian centers cannot use walking blood banks as we do not have a pre-screened population from which to draw, low-titer type O positive whole blood (LTOWB) can be used. One LTOWB unit is equivalent to one unit of PRBC and one unit of FFP. While LTOWB has been studied, the inclusion criteria for past studies has been less inclusive than in this trial, specifically excluding patients with severe traumatic brain injuries even if they also had exsanguinating hemorrhage. Furthermore, at Loma Linda University Medical Center we will have the opportunity to randomize patients to receive whole blood as their first transfusion, thus maximizing the potential benefits. Finally, we have the opportunity to study the coagulopathy associated with these patients by using viscoelastic testing.

b. Objectives

1. Evaluate PRBC equivalents transfused in each group in the first 24 hours (Primary outcome)
2. Evaluate total transfusion in each group in the first 24 hours (Secondary Outcome) including breakdown by FFP equivalents, platelet units, and cryoprecipitate
3. Evaluate 6 hour, 24 hour, and hospital mortality (Secondary Outcome)
4. Evaluate ICU outcomes in each group:
 1. ICU length of stay

- 2. Ventilator days
- 3. SOFA score on day of ICU discharge
- 4. Presence of ARDS?
- 5. Presence of TRALI?
- 6. Presence of DVT/PE?
- 7. Necessity for Dialysis?
- 8. Necessity for Tracheostomy?
- 5. Evaluate viscoelastic testing parameters in both groups when sent on arrival in ICU
 - 1. Percentage of patients with EXTEM clotting time > 80 sec
 - 2. Percentage of patients with EXTEM amplitude at 10 min < 40mm and FIBTEM amplitude at 10 min \leq 10mm
 - 3. Percentage of patients with EXTEM amplitude at 10 min < 40mm and FIBTEM amplitude at 10 min > 10mm

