 - 4. Percentage of patients with maximum thrombolysis > 15%
- 6. Interval analyses to be performed after 6 and 12 months with provision to continue the study out to 24 months.
 - 1. Stopping rule: A statistically significant difference in hospital mortality at 6 months or 12 months
 - 1. If in favor of LTOWB, consideration of trial termination and making LTOWB the primary standard of care for all trauma patients receiving emergency transfusion except for child-bearing age females (unless Rh immunoglobulin can be administered)
 - 2. If in favor of component therapy, consideration of trial termination and making component therapy the primary standard care for all trauma patients receiving emergency transfusion
- c. Procedures involved (Research Interventions)

*Chronological order of all research interventions, **distinguishing standard of care vs. research intervention.***

- 1. Level A trauma paged out with gender of patient
- 2. For female patients, care proceeds as normal
 - 1. Standard trauma cooler containing 4 units O- PRBC and 4 units FFP dispatched to trauma bay (if overall supply is short the first cooler may contain 2 units O- PRBC and 2 units FFP)
 - 2. Transfusion proceeds per trauma and ED team
 - 3. Patient data not included in the study

3. For male patients, the blood bank will randomize patients to the LTOWB group or the CT (component therapy) group based on a prespecified calendar-based randomization scheme by week:
 1. LTOWB: Cooler containing 2 or 4 units of LTOWB dispatched to trauma bay depending on supply
 2. CT: Standard trauma cooler containing 4 units O+ PRBC and 4 units FFP dispatched to trauma bay (if overall supply is short the first cooler may contain 2 units O+ PRBC and 2 units FFP)
 3. Transfusion proceeds per trauma and ED team
 4. Blood work (CBC, BMP, tox screen, ROTEM viscoelastic test, PT/INR, PTT, venous lactate) sent as per standard of care for all patients.
 5. Hemorrhage control and other diagnostic evaluations performed in all patients per standard of care.
 6. Patients arrive in ICU and have additional blood work (CBC, CMP, possibly ABG, ROTEM viscoelastic test, PT/INR, PTT, venous lactate, possibly fibrinogen) sent per standard of care by the ICU team.
 7. Clinical data on survival and transfusion monitored
- d. Alternative procedures, if any, that are not included in the study but might be advantageous to the subject. N/A

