University of Texas at Houston, patients were blood typed prior to inclusion in the study. Furthermore, all type B and AB patients were excluded, as were patients with significant traumatic brain injury or if they received more than 4 units of blood prior to randomization. Patients were also excluded if they could not, in the judgment of the attending surgeon, wait for blood typing. Thus, out of 357 patients who could have met criteria for inclusion, only 107 were actually randomized, introducing selection bias. In particular, the exclusion for the patients felt to be “too sick to wait” for blood typing may have excluded some sicker patients who would have benefited from whole blood. However, this study did demonstrate a reduction in transfusion volumes for patients after those with brain injury were excluded. (5)

As can be seen, the current field of literature leaves multiple unanswered questions that will be answered by the proposed study.

- 1) Does transfusion with low-titer O-positive whole blood reduce the amount of transfusion within 24 hours of arrival?
- 2) Does transfusion with low-titer O-positive whole blood reduce 6 hour, 24 hour, or hospital mortality?
- 3) What is the effect of low-titer O-positive whole blood transfusion on coagulopathy after trauma, as demonstrated by viscoelastic testing?
- 4) Is the potential benefit of transfusion with low-titer O-positive whole blood restricted only to patients receiving massive transfusion (6 units PRBC or more) or in all patients receiving emergency transfusion?
 - g. If an Investigational New Drug (IND) is involved, provide the following information: (1) name of drug, (2) source of drug, (3) dosage and schedule of administration, (4) status with Food and Drug Administration and IND#, (5) review of animal studies and previous human studies, (6) reported side effects

N/A

- h. For an approved drug used in an experiment, provide similar information: (1) name, (2) source, (3) dosage, (4) how administered, (5) side effects.

N/A

- i. If an Investigational Device (ID) is involved, provide the following information: (1) name of device, (2) manufacturer, (3) status with Food and Drug Administration and ID#, (4) review of animal studies and previous human studies, (5) reported adverse effects.

N/A

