9. DATA COLLECTION

Data collection procedures: to include lab evals, tests, specimen amounts and schedules, clinical assessments/schedule/follow up procedures, case report forms, data collection forms (with description of subject codes), study instruments, rating scales, interview guides.

RedCap Database to be created with the following data

Age (years)

Penetrating Trauma (0=no, 1=yes)

Penetrating Mechanism (1=stab, 2=gsw, 3=impalement, 9=other)

Blunt Mechanism (1=MVC, 2=Fall, 3=MCC, 4=ped vs auto, 5=assault, 9=other)

Scene transport (0=no, 1=yes)

Injury Severity Score (1-75)

Abbreviated Injury Score-Head (0-6)

Predominant site of hemorrhage (1=upper extremity, 2=lower extremity, 3=axilla, 4=groin, 5=head/neck, 6=chest, 7=abdomen, 8=pelvis, 9=other)

Tourniquet in Place (0=no, 1=yes)

Pre-LLUMC PRBC (# units)

Pre-LLUMC FFP (# units)

Pre-LLUMC PLT (# unitss

Pre-LLUMC Cryo (# units)

Pre-LLUMC Crystallloid (# liters)

Pre-LLUMC Cardiac Arrest? (0=no, 1=yes with ROSC, 2=yes without ROSC)

Arrival SBP (0 = in arrest)

Arrival HR (0 = in arrest)

Arrival Temperature (Celsius)

Arrival O2 saturation (0 = in arrest)

Arrival GCS (3-15)

Treatment Group (0 = Component Therapy, 1 = LTO+WB)

LLUMC ED WB (# units)

LLUMC ED PRBC (# units)

LLUMC ED FFP (# units)

LLUMC ED PLT (# unitss

LLUMC ED Cryo (# units)

LLUMC ED Crystallloid (# liters)

LLUMC ED Cardiac Arrest? (0=no, 1=yes with ROSC, 2=yes without ROSC)

LLUMC ED Thoracotomy (0=no, 1=yes)

LLUMC ED Laparotomy (0=no, 1=yes)

LLUMC ED Death? (0=no, 1=yes)

LLUMC ED ABG results

pH

Hgb

Lactate

LLUMC ED Hgb from CBC

LLUMC ED PLT count from CBC

LLUMC ED INR

LLUMC ED PTT

LLUMC ED Fibrinogen

LLUMC ED ROTEM results

EXTEM CT

EXTEM A10

If EXTEM A10 < 40mm, FIBTEM A10

EXTEM ML

Hemorrhage Control Environment (HCE) (0=none, patient died in ED, 1=none, patient direct to ICU, 2=OR, 3=IR, 4=OR and IR, 5=Hybrid OR)

LLUMC HCE WB (# units)

LLUMC HCE PRBC (# units)

LLUMC HCE FFP (# units)

LLUMC HCE PLT (# unitss

LLUMC HCE Cryo (# units)

LLUMC HCE Crystalloid (# liters)

LLUMC HCE Cardiac Arrest? (0=no, 1=yes with ROSC, 2=yes without ROSC)

LLUMC HCE Thoracotomy (0=no, 1=yes)

LLUMC HCE Laparotomy (0=no, 1=yes)

LLUMC HCE Pelvic Packing (0=no, 1=yes)

LLUMC HCE Neck Exploration (0=no, 1=yes)

LLUMC HCE Exploration for Axilla/Upper Extremity (0=no, 1=yes)

LLUMC HCE Exploration for Groin/Lower Extremity (0=no, 1=yes)

LLUMC HCE Death? (0=no, 1=yes)

LLUMC HCE ABG results #1 (first in HCE)

pH

Hgb

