
Lactate

LLUMC HCE ABG results #2 (last in HCE)

pH

Hgb

Lactate

LLUMC HCE ROTEM results #1 (first in HCE, if sent)

EXTEM CT

EXTEM A10

If EXTEM A10 < 40mm, FIBTEM A10

EXTEM ML

LLUMC HCE ROTEM results #2 (last in HCE, if sent)

EXTEM CT

EXTEM A10

If EXTEM A10 < 40mm, FIBTEM A10

EXTEM ML

LLUMC ICU/Floor Transfusion within first 24 hours (not including blood given prior to LLUMC, in LLUMC ED, and in LLUMC HCE)

LLUMC ICU WB (# units)

LLUMC ICU PRBC (# units)

LLUMC ICU FFP (# units)

LLUMC ICU PLT (# unitss

LLUMC ICU Cryo (# units)

LLUMC ICU Crystalloid (# liters)

LLUMC ICU ABG results

pH

Hgb

Lactate

LLUMC ICU Hgb from CBC

LLUMC ICU PLT count from CBC

LLUMC ICU INR

LLUMC ICU PTT

LLUMC ICU Fibrinogen

LLUMC ICU ROTEM results

EXTEM CT

EXTEM A10

If EXTEM A10 < 40mm, FIBTEM A10

EXTEM ML

Clinical Endpoints

Patient Dead on Arrival (0=no, 1=yes)

Patient Died within 6 hours of arrival (0=no, 1=yes)

Patient Died within 24 hours of arrival (0=no, 1=yes)

Patient Died Prior to Discharge (0=no, 1=yes)

Duration of Mechanical Ventilation (Days)

Duration of ICU Stay (Days)

Duration of Hospital Stay (Days)

Presence of ARDS?

Presence of TRALI?

Presence of DVT/PE?

SOFA Score on Day of ICU Discharge

Need for Dialysis During Hospitalization (0=no, 1=yes)

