13. BENEFIT(S)

It is possible that patients transfused with LTO+WB may experience improved resolution of coagulopathy. As such it is possible that they may experience either reduced transfusion or even a survival benefit. Thus far, available literature has not demonstrated a survival benefit consistently, nor has it consistently demonstrated reduced need for transfusion. As such, it is felt by the investigators that clinical equipoise still exists between the two randomized treatment arms.

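### Objective 5 compares ROTEM on ICU arrival only and leaves the stored ED ROTEM unused, which costs precision and leaves resolution of coagulopathy unmeasured

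*Combined protocol and SAP*

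**What the plan says.** All references are to the combined protocol and SAP.

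- **Endpoint (section 8.b, objective 5):** "Evaluate viscoelastic testing parameters in both groups when sent on arrival in ICU". Four percentages follow: prolonged EXTEM clotting time, two combined EXTEM/FIBTEM amplitude categories, and high maximum lysis. Objectives 1–3 are labelled primary or secondary; objective 5 carries no label.
- **Research question (section 8.f, question 3):** "What is the effect of low-titer O-positive whole blood transfusion on coagulopathy after trauma, as demonstrated by viscoelastic testing". It does not ask for a change from baseline.
- **Possible benefit (section 13):** "It is possible that patients transfused with LTO+WB may experience improved resolution of coagulopathy".
- **Earlier sample (section 8.c, step 3.4):** "Blood work (CBC, BMP, tox screen, ROTEM viscoelastic test, PT/INR, PTT, venous lactate) sent as per standard of care for all patients". The step before it, 3.3, reads "Transfusion proceeds per trauma and ED team". ICU blood work comes later, at step 3.6.
- **Data (section 9):** "LLUMC ED ROTEM results" and "LLUMC ICU ROTEM results" have the same entries: EXTEM CT, A10 and ML, and FIBTEM A10 when EXTEM A10 is below 40 mm. Products given before arrival are recorded too, for example "Pre-LLUMC PRBC (# units". No field places the ED sample before or after the first LLUMC unit.
- **Analysis (section 11):** a nonparametric comparison of medians. ROTEM is not mentioned, and no covariate, stratum or change score is defined for it.

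**The concern.** Resolution is a change from an earlier state. A single percentage on ICU arrival counts a man who was never coagulopathic in the same way as a man whose coagulopathy was corrected. It also counts persisting and new coagulopathy together. The plan collects what it needs to tell these apart and then specifies no analysis that links the two time points.

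Two things are at stake. The ICU comparison carries variation from the arrival state that the ED value could partly remove. An effect confined to men who arrive coagulopathic is also diluted by those who do not.

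The order of steps 3.3 and 3.4 adds a practical difficulty. If the ED sample is drawn after the first unit, it already reflects treatment and is not a baseline.

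**Working it through.** The plan gives no sample size, power or expected rate for objective 5, so there is no figure to reproduce. The 190 in section 6 belongs to the primary outcome. Everything below uses **assumed** rates and correlations. The plan's 200 patients give at most 100 per arm if allocation is 1:1 (the ratio is not stated). Where 80 per arm is used, it is an assumed number with an ICU ROTEM.

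**1. Is the ICU-only comparison biased?** A simulation with no treatment effect was run 20,000 times with 100 per arm, individual 1:1 randomisation, 60% persistence and 5% new cases. The mean difference was about 0. Type I error was 5.0% at 30% ED prevalence and 5.2% at 50%. The comparison is not biased.

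**2. How large is chance imbalance at arrival?** SD = sqrt(2p(1−p)/n).
- n = 80, p = 0.30: sqrt(2 × 0.21/80) = 0.0725, about 7 points. An imbalance of 7 points or more, in either direction, occurs in about one trial in three.
- n = 100, p from 0.20 to 0.50: 1.96 × SD is 11 to 14 points.

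Only part of this reaches the ICU result. With equal prevalence at both times, the share passed on is the correlation φ between the two yes/no results (step 3). A 7.25-point imbalance then moves the ICU contrast by 7.25 × 0.248 = 1.8 to 7.25 × 0.394 = 2.9 points. The usual standard error already allows for it.

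**3. What would adjustment gain?** Residual variance is 1 − r², and the equivalent gain in patients is 1/(1 − r²) − 1.
- Continuous parameters, r = 0.4: 1/0.84 − 1 = 19%. At r = 0.6: 1/0.64 − 1 = 56%.
- Threshold percentages: cut a bivariate normal at 30% abnormal both times, with φ = (P(both abnormal) − 0.09)/0.21. For r = 0.4, φ = (0.1420 − 0.09)/0.21 = 0.248, variance falls by 6.1%, and the gain is about 6.5%. For r = 0.6, φ = (0.1727 − 0.09)/0.21 = 0.394, variance falls by 15.5%, and the gain is about 18.4%.

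Objective 5 is written in percentages, so the second line is the relevant one for its endpoints as they stand.

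**4. How strong is the dilution?** Assume 100 per arm, 60% versus 40% of men abnormal in the ED still abnormal in the ICU, and 5% new cases in both arms. At 30% ED prevalence:
- ICU percentages are 0.30 × 0.60 + 0.70 × 0.05 = 21.5% and 0.30 × 0.40 + 0.70 × 0.05 = 15.5%. The difference is 6 points, and power is 19% (two-sided 5%).
- Among the 30 men per arm abnormal in the ED, the difference stays at 20 points, and power is 34%.

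Across prevalences of 20–50%, the ICU difference is 4–10 points with power 13–35%. The comparison among men abnormal in the ED has power 24–52%. Both are low, but only the second describes resolution.

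**The case against.** The strongest reply is that nothing here is an error. Arrival coagulopathy is balanced in expectation, and a between-arm comparison on ICU arrival does address question 3 as written. This stands. A reader might infer that the treatment effect is confounded with the arrival state; step 1 of the working shows that it is not, given sound randomisation. A reader might also infer that the plan promises resolution as a benefit. Section 13 words it only as a possibility, and no endpoint is built on it.

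A second reply is that adjustment can do harm. Whether the ED sample precedes the first LLUMC unit is settled after allocation. If that timing differs by arm and by severity, restricting to pre-unit samples, or coding the rest with a missing-baseline indicator, can introduce a small bias. This also stands. It is why the adjusted analysis should support the unadjusted one and not replace it.

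Third, draw times may be recoverable from the source record. Sections 10 and 15 keep a master list linking study ID to MRN until data collection is complete. So the documents do not support the stronger reading that a baseline could never be identified. A field filled in at data entry is simply more reliable.

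Finally, products given before arrival may affect even a pre-unit ED sample. These are recorded and are not part of the trial treatment, so such a sample can still serve as a covariate, though not as an untreated state.

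**Conclusion.** The point holds as a loss of precision and of interpretability, not as bias. The plan stores ED and ICU ROTEM with the same parameters and specifies no analysis joining them, so it cannot report resolution.

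The possible gain is about 19–56% more effective patients for continuous parameters and about 6–18% for the threshold percentages. It is smaller to the extent that pre-unit samples are missing, a share the documents do not give. These figures assume ED–ICU correlation of 0.4–0.6, 30% abnormal at both times for the percentages, and individual randomisation; the plan allocates by calendar week. No document figure supports the prevalence or the correlation. The primary outcome, the sample size and the stopping rule are unaffected.

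**What to change.** 1. Keep the unadjusted ICU-arrival comparison in objective 5 as it is.
2. Add to objective 5 and section 11 a prespecified supportive comparison of ICU EXTEM CT, A10 and ML, and of the four threshold categories, each adjusted for the same ED parameter. Section 11 covers only medians, so name the method, for example a linear model for the continuous values and a stratified difference in proportions for the categories. The combined categories can be derived from the ED entries, because FIBTEM A10 is recorded whenever EXTEM A10 is below 40 mm.
3. Report by arm the percentage normal in the ICU among men abnormal in the ED.
4. Add one yes/no REDCap field: ED ROTEM drawn before the first LLUMC unit. Use only pre-unit samples as baseline for items 2 and 3, report their share by arm, and treat both results with caution if that share differs.

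The cost is one field and a few sentences of analysis text, with no new test and no change in care. Samples drawn after the first unit cannot serve as baseline. The change does not deal with men who die before the ICU or have no ICU ROTEM; the plan should say separately how they are handled.

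### Objective 5 compares ROTEM abnormalities only in patients who reach the ICU and are tested, so a difference in survival to the ICU can dilute, hide or, if large, reverse an effect on coagulopathy.

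*Combined protocol and SAP*

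**What the plan says.** Study question 3, at the end of section 8f, is: "What is the effect of low-titer O-positive whole blood transfusion on coagulopathy after trauma, as demonstrated by viscoelastic testing". It is not limited to patients who reach the ICU.

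The objective that answers it (section 8b, objective 5) is to "Evaluate viscoelastic testing parameters in both groups when sent on arrival in ICU". It has four endpoints, each a percentage, for example "Percentage of patients with EXTEM clotting time > 80 sec". No denominator is defined: patients allocated, patients reaching the ICU and patients tested are all possible readings. The wording of the objective points to the last.

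The data form (section 9) provides for death between arrival and the ICU. The destination field reads "Hemorrhage Control Environment (HCE) (0=none, patient died in ED, 1=none, patient direct to ICU", and there is a separate item "LLUMC HCE Death? (0=no, 1=yes". Section 13 allows for an effect on survival: "As such it is possible that they may experience either reduced transfusion or even a survival benefit".

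Sections 5 and 11 set aside only patients who are dead on arrival, and section 5 gives survivor bias as the reason. Neither section has a rule for a patient who dies after arrival but before the ICU sample, or for a living patient with no ICU sample. Earlier ROTEM results are recorded, from the ED and from the HCE (such as "LLUMC HCE ROTEM results #2 (last in HCE, if sent"), but no objective or analysis uses them.

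**The concern.** Reaching the ICU alive and being tested both happen after allocation. If coagulopathic patients are more likely to die early, and one arm keeps more of them alive, that arm brings more abnormal ROTEM results into the percentages because it did better. The arms then differ in who is measured as well as in treatment, and allocation no longer protects the comparison.

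The protocol's own hypothesis makes this relevant: section 13 links better resolution of coagulopathy with possible better survival. At stake is the answer to one of the four study questions. A real improvement could be reported as small or absent, or in an extreme case as harm. If survival to the ICU were worse with whole blood, the error would run the other way and flatter it.

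**Working it through.** The plan states no rate, effect size or power for the ROTEM endpoints, so there is no figure to reproduce. The calculations below show the mechanism and its likely range. All rates are assumptions.

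**Main illustration.** Let p be the true proportion abnormal among all non-DOA patients in an arm, d the proportion dying before the ICU, and 0.9 the assumed proportion of those deaths that are coagulopathic. Among ICU arrivals, all assumed tested:

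observed rate = (p − 0.9d) / (1 − d)

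Component therapy (CT) is held at p = 0.40 and d = 0.15: (0.40 − 0.135)/0.85 = 31.2%. For whole blood (LTOWB) with d = 0.05:
- no true effect: (0.40 − 0.045)/0.95 = 37.4%
- true 10-point benefit: (0.30 − 0.045)/0.95 = 26.8%
- true 5-point benefit: (0.35 − 0.045)/0.95 = 32.1%

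Other values of d for LTOWB, in the same way:

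| Pre-ICU death, CT v LTOWB | No true effect: observed (spurious harm) | True 10-point benefit: observed (benefit seen) | True 5-point benefit: observed (benefit seen) |
|---|---|---|---|
| 15% v 15% | 31.2% v 31.2% (0) | 31.2% v 19.4% (11.8) | 31.2% v 25.3% (5.9) |
| 15% v 12% | 31.2% v 33.2% (2.0) | 31.2% v 21.8% (9.4) | 31.2% v 27.5% (3.7) |
| 15% v 10% | 31.2% v 34.4% (3.3) | 31.2% v 23.3% (7.8) | 31.2% v 28.9% (2.3) |
| 15% v 5% | 31.2% v 37.4% (6.2) | 31.2% v 26.8% (4.3) | 31.2% v 32.1% (−0.9) |

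With equal deaths there is no spurious difference. A true difference is only re-expressed on the smaller base of ICU arrivals (10/0.85 = 11.8; 5/0.85 = 5.9).

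**Check with a second model.** Let S be the proportion alive to the ICU, p the abnormal rate in patients who would reach the ICU in either arm, and r the rate in patients who reach it only with LTOWB. Assume no one reaches it only with CT.

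observed LTOWB rate = [S_CT × p_LTOWB + (S_LTOWB − S_CT) × r] / S_LTOWB

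Take p = 30% with CT, and r = 60%, 80% and 100% in turn.
- Deaths 10% v 5%, true 5-point benefit: observed LTOWB 26.8%, 27.9%, 28.9%. The benefit is diluted but not reversed.
- Deaths 20% v 10%, true 5-point benefit: 28.9%, 31.1%, 33.3%. The sign changes once r exceeds (0.30 × 0.90 − 0.25 × 0.80)/0.10 = 70%.
- Deaths 30% v 15%, true 10-point benefit: 27.1%, 30.6%, 34.1%. The sign changes once r exceeds (0.30 × 0.85 − 0.20 × 0.70)/0.15 = 77%.
- Deaths 20% in each arm, same patients surviving: no distortion.

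**Does a composite help?** Count death before the ICU sample as failure: rate = d + (p − 0.9d). With the 15% v 5% inputs, CT is 0.15 + 0.265 = 41.5%. LTOWB is 0.05 + 0.355 = 40.5% with no true effect, 0.05 + 0.305 = 35.5% with a 5-point benefit and 0.05 + 0.255 = 30.5% with a 10-point benefit. The spurious harm disappears and the direction is right in each case. Part of each difference is now survival.

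**The case against.** **The largest figures need a large survival gap.** This stands. A threefold difference in pre-ICU death is a high-end case, and a smaller gap costs a few points. Section 13 says the literature has not consistently shown a survival benefit, and section 8f cites comparisons without an unadjusted difference.

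**A large gap would be visible.** With about 100 per arm (200 planned, equal split assumed), 15 v 5 deaths gives a Fisher p of about 0.03, and objective 3 reports mortality by arm. The 6-point bias also lies within a simple 95% half-width of about 14 points: 1.96 × √(0.312 × 0.688/85 + 0.374 × 0.626/95) = 0.138. This softens the point. It does not tell a reader how far to discount the ROTEM percentages, and a smaller gap could pass unnoticed.

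**Testing adds little selection.** A reader might infer that the choice to send the test matters as much as survival. The documents do not support that. Section 8c lists ICU ROTEM as standard-of-care blood work, and the qualifier for optional tests is attached to the blood gas and fibrinogen only. Nor are ROTEM data confined to ICU survivors: section 8c has an ED sample sent for all patients. But no analysis uses it, and it is not timed against the first study unit, so it may be a pre-treatment value.

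**A composite for every threshold would be a poor remedy.** This also stands. The second and third endpoints are mutually exclusive patterns, so the same death would count as failure on both. Deaths from brain injury, which this trial does not exclude, would count as coagulopathy four times.

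**Conclusion.** The concern holds as a conditional one. If survival to the ICU differs between arms, the ROTEM comparison is not a randomised one, and nothing else in the plan repairs it. On the main assumptions, survival gaps of 3 to 10 points give a spurious harm of about 2 to 6 points and reduce a true 10-point benefit to about 9 to 4. Reversal needs a large gap: in the cases tried, 10 to 15 points, with most of the additional survivors coagulopathic. Deaths that are equal and of similar patients cause no spurious difference. Death before the ICU is the main source, and absent tests among ICU arrivals are probably a minor one.

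A reader might go further and conclude that the coagulopathy result will be misleading. The documents do not support this, because they give neither pre-ICU death rates nor ROTEM abnormality rates. Objective 5 does not enter the primary outcome, the sample size or the stopping rule, so those are untouched. The change is worth making because it answers a stated study question more safely at little cost.

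**What to change.** 1. Keep the four ICU percentages, state their denominator, and label them descriptive and conditional on reaching the ICU and being tested.
2. Add one analysis, in all non-DOA patients, of any of the ROTEM abnormalities on ICU arrival or death before the ICU sample, with the components shown separately by arm. Do not build a composite for each threshold.
3. Report by arm the numbers who died before the ICU, reached the ICU and were tested.
4. For living patients with no ICU sample, show best-case and worst-case bounds. As a sensitivity analysis use the last HCE ROTEM; use the ED ROTEM only if it is known to have been drawn after the first study unit.

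The cost is analysis wording. ED and HCE deaths and the ED, HCE and ICU ROTEM results are already on the form, and no new test is needed. The form lists no sampling times, so using the ED result would need that check in the record. The drawback is that the composite mixes death, including death from brain injury, with coagulopathy. It supports the ICU percentages and does not replace them.
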